4.1. Primary and secondary endpoint

The **primary endpoint** of the study is the ERRs of these two formulations of mebendazole against hookworm assessed before and 14 to 21 days post-treatment using the duplicate Kato-Katz technique. **Secondary endpoints** are the CR against hookworm, CRs and ERRs against *A. lumbricoides* and *T. trichiura* (assessed 14-21 days post-treatment), safety (assessed 3 and 24 hours post-treatment), and acceptability and age-appropriateness of the two formulations of mebendazole (assessed during treatment). **Exploratory endpoints** are how well caregivers understood the clinical trial's informed consent form and its content, and which of the informing methods increase caregivers understanding the most (assessed during the informed consenting process).

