4.4. Measure to minimize bias

Study participants eligible for treatment will be randomly assigned to one of the two treatment arms using a computer-generated stratified block randomization code. The random allocation sequence with varying random blocks of four or eight and stratified by 2 levels of baseline infection intensity (light: 1-1999 EPG, and moderate plus heavy: ≥ 2000 EPG hookworm infections) will be provided by a statistician. Both treatment arms will have an equal number of participants with light infection intensity, although the number of light *versus* moderate/heavy infections are not expected to be equal within each arm, depending on the distribution of infection intensity in the recruited cohort.

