8.1. Definition of primary endpoint

The primary endpoint of this study is the ERR of mebendazole against hookworm assessed 14 to 21 days post-treatment using the duplicate Kato-Katz thick smear method.

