8.2. Justification of number of trial subjects

Because the primary outcome – difference in egg reduction rates (ERR) – does not follow a known distribution we ran a series of conservative simulations using data from Speich *et al.* [22] to determine the required sample size. An initial round of simulations showed that differences in ERRs are associated with substantial higher power compared to CRs. We used Monte Carlo resampling techniques to simulate CR of 10 and 20%, respectively, which translates roughly into ERRs of 38% and 64%. We estimated that 160 patients per arm are required to detect a statistical significant difference with 80% power. To account for potential loss to follow up (which was low in our previous studies in this setting) of 10% and to include a safety margin of 14% we aim to recruit in total 200 participants per trial arm.

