8.3. Description of statistical methods

The primary analysis will use the full analysis set (available case population) according to the intention to treat principle defined as all randomized subjects which provide any follow-up data. Only subjects which were negative at baseline and erroneously randomized will be excluded from the analysis. Palatability and ease of swallowing are critical attributes in children; therefore, a per-protocol analysis will be conducted additionally to disentangle drug efficacy from adherence effects.

Geometric mean egg counts will be calculated for the different treatment arms before and after treatment to assess the corresponding ERRs. The ERR will be calculated as:

$$ERR = 1 - \frac{\frac{1}{n} e^{\sum \log(EPG_{follow-up} + 1)} - 1}{\frac{1}{n} e^{\sum \log(EPG_{baseline} + 1)} - 1}$$

Bootstrap resampling with 5,000 replicates will be used to calculate 95% confidence intervals (CIs) for ERRs and the difference between the two ERRs. Superiority will be claimed if the 95% confidence interval of the difference in ERRs does not include unity (primary hypothesis).

Differences in CRs will be assessed using unadjusted logistic regressions. In a subsequent analysis an adjusted logistic regression (adjustment for age, sex, weight and strata) will be performed.

AEs will be evaluated descriptively as the difference of proportion reporting AEs before and after treatment.

9. Duties of the investigator

The investigators are responsible for an adequate data quality. Prior to the initiation of the study, a short investigator's meeting will be held with the investigators and their study coordinators and a member from Swiss TPH. This meeting will include a detailed discussion of the protocol, performance of study procedures (SOPs from previous studies available on site), CRF completion, and specimen collection and diagnostic methods.

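### The lead analysis of the secondary hookworm cure-rate endpoint ignores the stratification factor, and continuous baseline egg count is in neither planned cure-rate model

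*Combined protocol and SAP*

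**What the plan says.** Section 8.3 plans two analyses of cure rate. The first is unadjusted: "Differences in CRs will be assessed using unadjusted logistic regressions". After it, "an adjusted logistic regression (adjustment for age, sex, weight and strata) will be performed". The synopsis repeats both. Neither place says which result governs if they differ; the order implies that the unadjusted one leads.

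Section 4.4 says that allocation is "stratified by 2 levels of baseline infection intensity", with the levels given as "light: 1-1999 EPG, and moderate plus heavy: ≥ 2000 EPG hookworm infections". The word strata in the adjusted model therefore means baseline egg count in two levels.

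Baseline egg count is available as a number for every eligible child. Section 5.2 requires two stool samples at baseline, section 4.3.1 prepares two smears from each, and section 4.3.3 sums the four counts and multiplies by six to give EPG.

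On the standing of the endpoint, section 4.1 has: "Secondary endpoints are the CR against hookworm", followed by several others with no ranking. Section 8.1 has: "The primary endpoint of this study is the ERR of mebendazole against hookworm assessed 14 to 21 days post-treatment". Section 8.2 sizes the trial on the ERR difference and acknowledges that CR has less power.

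**The concern.** Cure is defined in section 4.3.3 as no eggs in the follow-up samples. A child who starts with fewer eggs plausibly reaches zero more easily, and the plan itself treats intensity as important enough to stratify on. If baseline count predicts cure, a lead model without it gives up some precision and leaves the treatment estimate exposed to chance differences in egg count between arms.

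The later adjusted model may do little to repair this. If most children fall below 2000 EPG, the two-level stratum hardly separates them, and the stratified randomisation does not balance egg count within the large lower stratum. At stake is the precision of one secondary comparison, and which of two CR results is to be believed if they disagree.

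**Working it through.** **Inputs from the documents.** CRs of 10% and 20%, and 200 children per arm with 10% loss (section 8.2), so 200 × 0.90 = 180 evaluable per arm. Stratum cut at 2000 EPG (section 4.4). Minimum baseline of 50 EPG (section 5.2; sections 4.3.1 and 4.3.3 use 100). A two-sided 5% level is inferred from the 95% CI in section 8.3; no level is stated for CR.

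**The plan's own figure.** Section 8.2 says: "We estimated that 160 patients per arm are required to detect a statistical significant difference with 80% power". It comes from resampling external egg-count data and concerns ERR, so it can be neither reproduced nor refuted here. The step to 200 does reproduce: 160 × 1.10 × 1.14 = 200.6, or 160 × 1.24 = 198.4. No power is stated for CR.

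**Unadjusted CR power.** Power = Φ{[0.10·√n − 1.96·√(2 × 0.15 × 0.85)] / √(0.10 × 0.90 + 0.20 × 0.80)} = Φ{[0.10·√n − 0.990] / 0.5}.

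- n = 160: Φ(0.550) = 70.9%
- n = 180: Φ(0.704) = 75.9%
- n = 200: Φ(0.849) = 80.2%

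Reaching 80% needs 199 per arm.

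**Gain from log baseline EPG, by simulation.** The documents give neither the distribution of baseline EPG nor its relation to cure, so both are assumed:

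- EPG is log-normal, truncated at 50. Distribution A has geometric mean 250 and log SD 1.0 before truncation, which puts 2.0% of children at 2000 EPG or more. Distribution B has 500 and 1.2, which puts about 12.7% there.
- The odds of cure fall by a factor OR for each SD of log EPG, with overall CRs held at 10% and 20%.
- Age, sex and weight are not prognostic.
- Allocation is balanced within stratum, with 4,000 trials per scenario and Wald tests. All models are fitted to the same simulated trials. The Monte Carlo error of each power is √(0.76 × 0.24 / 4000) ≈ 0.7 points.

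Power (%) at 180 per arm, distribution A / distribution B:

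| OR per SD | Unadjusted | Planned adjusted | Treatment + log EPG | Gain over unadjusted (points) |
|---|---|---|---|---|
| 1.0 | 75.2 / 76.5 | 75.2 / 76.5 | 75.0 / 76.6 | −0.2 / 0.1 |
| 1.5 | 76.7 / 75.3 | 76.4 / 75.6 | 76.8 / 76.1 | 0.1 / 0.8 |
| 2.0 | 76.5 / 77.3 | 76.4 / 77.5 | 78.1 / 79.1 | 1.6 / 1.8 |
| 3.0 | 76.1 / 75.2 | 75.5 / 75.4 | 80.9 / 80.4 | 4.8 / 5.2 |
| 4.0 | 76.5 / 77.8 | 75.8 / 78.1 | 83.1 / 84.0 | 6.6 / 6.2 |

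Under distribution A, the gains at 160 and 200 per arm were 2.5 and 2.0 points at OR 2, and 3.6 and 3.4 points at OR 3. The planned adjusted model stays within 1 point of the unadjusted one throughout, so under these distributions the two-level stratum recovers almost nothing. With no treatment effect (distribution A, OR 2 and 3), rejection rates were 4.2% to 5.3% across all models.

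**Analytic check.** For the standardised difference, power = Φ{0.10 / √[0.25(1 − R²)/180] − 1.96}, where R² is the share of outcome variance removed by log EPG.

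- R² = 0: 76.5%
- OR 1.5 (R² = 0.018): 77.3%
- OR 2 (R² = 0.049): 78.6%
- OR 3 (R² = 0.108): 81.1%
- OR 4 (R² = 0.156): 83.2%

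This agrees with the simulation.

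**What these odds ratios mean.** Under distribution A, OR 2 implies cure in the 10% arm of about 17%, 9% and 4% from the lowest to the highest third of baseline EPG. OR 3 implies about 20%, 7% and 2%.

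**Chance imbalance.** Without balancing, the 95% range of the arm difference in mean log EPG is ±1.96·√(2/180) = ±0.21 SD; stratification narrows this little if few children are in the upper stratum. The shift in the treatment log odds ratio is about 0.21 × ln 1.5 = 0.08 at OR 1.5 and 0.21 × ln 3 = 0.23 at OR 3. The planned effect is ln[(0.20/0.80)/(0.10/0.90)] = ln 2.25 = 0.81.

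**The case against.** The strongest reply is that nothing here is an error. Unadjusted logistic regression gives a valid marginal comparison, the rejection rate under no effect is close to 5%, stratification limits gross imbalance, and an adjusted analysis is already planned. All of that stands. It makes this a question of efficiency and pre-specification, and it keeps the point minor.

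Three stronger readings are tempting, and the documents do not support them.

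- A reader might infer that the adjusted model leaves out baseline egg count. It does not: the strata are that count, cut at 2000 EPG. Only the continuous form is missing. How coarse the cut is in practice is unknown, because section 4.4 says only that the two levels are not expected to be equal in size.
- A reader might infer a loss of several points of power. That needs an odds ratio of about 3 or more per SD of log EPG, and the documents report no such association.
- A reader might infer that CR is the leading secondary endpoint and misses a power target. Section 4.1 sets no ranking, and there is no CR target to miss. The 76% assumes the full 10% loss, while section 8.2 calls earlier losses low; at 200 per arm it is 80.2%.

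Nor is the change free. The adjusted odds ratio is conditional and differs from the marginal one. Only about 180 × 0.10 + 180 × 0.20 = 54 cures are expected, so the model must stay small. None of this argues against using a baseline value that is already collected.

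**Conclusion.** The point holds in a limited form. The lead CR model ignores the stratification factor, and continuous baseline EPG is in neither CR model. At 180 per arm with CRs of 10% and 20%, adding log baseline EPG to the lead model gains about 0 to 2 points of power for an odds ratio of 2 or less per SD, and about 5 to 7 points for 3 to 4. These figures rest on an assumed log-normal baseline and an assumed relation with cure, so the range is the result and no single value in it is established. Correction for chance imbalance in EPG within strata is a further benefit, and its size depends on the same association. The primary ERR analysis, whose formula already uses baseline EPG, is untouched. Severity is minor.

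**What to change.** In section 8.3, and in the matching synopsis entry:

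- Make the lead hookworm CR analysis a logistic regression on treatment and log baseline EPG, retaining the randomisation stratum if it is estimable.
- Fix in advance what happens if it is not, for example dropping the stratum term when the upper level contains no cures. This could occur: if 2% of 360 children (about 7) were in that level, even an average cure probability of 15% would give no cures with probability 0.85⁷ = 0.32.
- Report the standardised (marginal) CR difference with a 95% CI, by a named method such as the bootstrap, beside the conditional odds ratio.
- Keep the unadjusted model as a sensitivity analysis, and state that the log-EPG model governs if they differ.

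The cost is a few lines of text and a modest amount of programming, with no new data. Under section 9.1 the amendment has to be written, signed by the principal investigator and approved by the ethics committees before it takes effect. It should be settled before outcome data by arm are seen.

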1.4. Synopsis

Study title	Efficacy and safety of a new chewable tablet of mebendazole versus the swallowable, standard mebendazole tablet against hookworm infections in children: a randomized controlled trial
Short title	Efficacy of chewable and swallowable MEB tablets
Protocol number, version and date	V4.01, 26.08.2019
Trial registration	Will be registered on http://clinicaltrials.gov/
Study type	Phase 2 trial
Sample size	400
Indication	Hookworm infection
Investigational product and reference treatment	Mebendazole
Study rationale	To provide evidence on the safety and efficacy of a chewable tablet of mebendazole compared to the standard tablet in preschool- and school-aged children infected with hookworm.
Study objectives	
To compare the efficacy and safety of two formulations of mebendazole: (i) single dose of 500 mg chewable tablet, and (ii) single dose of 500 mg standard swallowable tablet of mebendazole in participants aged 3-12, inclusive, infected with hookworm.
 
The primary objective is to comparatively assess the efficacy in terms of egg reduction rates (ERRs) against hookworm infections using the duplicate Kato-Katz thick smear method on two stool samples among preschool- and school-aged children 14-21 days after the following oral treatment regimens:
 
 • 500 mg swallowable tablet of mebendazole • 500 mg chewable tablet of mebendazole

	
The secondary objectives of the trial are:
 
 • To evaluate the safety and tolerability of the two formulations • To evaluate the cure rates (CRs) of the two formulations against hookworm • To determine the CRs and ERRs against Ascaris lumbricoides and Trichuris trichiura • To investigate the acceptability and age-appropriateness of both formulation when administered to children between 3 and 12 years of age 
The exploratory objectives of this study are:
 
 • To assess how well caregivers understand the clinical trials aim, procedures, their rights, risks and potential benefits • To compare the effect of different methods of providing information on their understanding of the clinical trial
Study design	Randomized controlled, open-label, parallel-group, superiority trial (outcome assessors are blinded).
Study product / intervention	Administration of a single oral dose of a 500 mg chewable tablet of mebendazole
Comparator(s)	500 mg swallowable tablet of mebendazole

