Key inclusion / exclusion criteria	
Inclusion: preschool- and school-aged children (3-12 years) with hookworm with at least two slides of quadruplicate Kato-Katz thick smears positive and infection intensities of at least 50 eggs per gram of stool (EPG), with written informed consent signed by the caregiver, able and willing to be examined by a study physician before treatment and to provide two stool samples at baseline.
 
Exclusion: pregnant, any abnormal conditions or history of major systemic or chronic illnesses, severely anaemic (Hb < 80 g/l), received anthelmintic treatment or metronidazole within the past four weeks, or is attending any other clinical trial during this

	study.
Primary endpoints	ERRs on hookworm, assessed 14-21 days post treatment
Secondary endpoints	CRs against hookworm, assessed 14-21 days post treatment CRs and ERRs against A. lumbricoides and T. trichiura Safety, assessed 14-21 days post treatment Acceptability and age-appropriateness of the tablets, assessed during treatment
Exploratory endpoints	Caregivers understanding of the clinical trial in general and by caregiver group, assessed during the informed consenting procedure
Interim analyses	None
Study duration	12 weeks total; up to 10 weeks per participant
Schedule	02/2019 of first-participant in (planned) 05/2019 of last-participant out (planned)
Study site	Wawi, Mvumoni, Bwagamoyo, Piki and Mzambarauni schools, Pemba, Tanzania
Measurements & procedures	A first stool sample will be collected and if the participant is found positive for hookworm a second stool sample will be requested, if possible the next day. The medical history of the participating individuals will be assessed with a standardized questionnaire contained in the case report form, in addition to a clinical and physical examination carried out by the study physician before treatment. This examination also includes pricking subjects' fingers to measure haemoglobin (Hb) levels and, in the case of female participants aged ≥ 10 years, a urine pregnancy test. Randomization of participants into the two treatment arms will be stratified according to intensity of infection. Participants will be interviewed before treatment for clinical symptoms and 3, and 24 hours after treatment to assess occurrence of adverse events (AEs). The efficacy of the treatment will be determined 14-21 days post-treatment by

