The European Medicines Agency recommends swallowable tablets for children aged 6 years or older [12] and the WHO recommends only administering chewable tablets to children aged 5 or younger [13]. Indeed, in the UK, children aged 6 years and older are willing to take tablets of any size (Ranmal et al 2016). However, children as young as 3 years old have been found to easily swallow conventional tablets [14-16] and children above 6 years of age have reported difficulties [17]. A survey in Nigeria found that caregivers prefer liquid formulations because they are sweet and do not require further preparation (Orubu et al 2017). However, solid tablets have significant advantages: they have a lower risk of incorrect administration (Walsh et al 2011) and are easily stored, transported and distributed (WHO 2012). In low-resource settings, as are most of those requiring preventive chemotherapy, the ease of storage, transport and distribution of the drugs is particularly important. Thus, ideally, a formulation which could be transported and stored in a solid form but administered in a semi-solid or liquid form could be a solution for young children.

The WHO's call for a more child-friendly formulation of mebendazole resulted in the development of a chewable 500 mg tablet by Johnson & Johnson (Vermox™). In the case of young children, the WHO recommends crushing the tablet on a spoon, adding 2-3ml of clean

water and waiting for two minutes until it becomes a soft mass with semi-solid consistency which can more easily be administered. On the other hand, WHO recommends that older children should be encouraged to chew it (but never swallow it whole). Randomized, double-blind, placebo-controlled trials which took place in Ethiopia and Rwanda have established safety and effectiveness against *A. lumbricoides* and *T. trichiura* in children aged 1-16 years [18, 19]. The efficacy of this chewable tablet of mebendazole against hookworm has not yet been studied. This formulation aims at making it easier for pre-school and school-aged children (PSAC and SAC) to swallow the drug but its acceptability has not yet been explored. Thus, in this study we will compare the efficacy, safety, and acceptability and age-appropriateness of the two tablets (swallowable and chewable) of mebendazole and explore caregivers' perceptions about both formulations.

3. Trial objective and purpose

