The overall goal of this study is to determine if a chewable formulation of mebendazole is superior to a swallowable formulation tablet of mebendazole (standard of care) against hookworm in children.

We hypothesize that the chewable formulation of mebendazole has a higher efficacy against hookworm infections than the swallowable one. Better absorption and bioavailability as well as better palatability are expected to contribute to superior efficacy.

The **primary objective** of the study is to compare the egg reduction rates (ERRs) of two different mebendazole formulations against hookworm in children (3 - 12 years old): (i) 500 mg of a single chewable mebendazole tablet and (ii) 500 mg of a single solid mebendazole tablet.

The **secondary objectives** of the trial are:

- To evaluate the safety and tolerability of the two formulations
- To evaluate the CR of the two formulations against hookworm
- To determine the CRs and ERRs against *Ascaris lumbricoides* and *Trichuris trichiura*
- To investigate the acceptability and age-appropriateness of both formulation when administered to children between 3 and 12 years of age

The **exploratory objectives** of this study are:

- To assess how well caregivers understand the clinical trials aim, procedures, their rights, risks and potential benefits

- To compare the effect of different methods of providing information on their understanding of the clinical trial

4. Methodology

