5.6. Concomitant therapy

All medications taken one month before and during the study period until the last stool examination between day 14 and 21 (follow-up) must be recorded with indication, dose regimen, date and time of administration.

Medication(s)/treatment(s) permitted during the trial:

- Analgesics and antipyretics are allowed to be given to the subjects in case of fever, antiemetics to prevent nausea and vomiting and/or antibiotics to prevent or treat bacterial superinfection.

Medication(s)/treatment(s) NOT permitted during the trial:

- No other active drugs against helminths are permitted during the trial.
- Metronidazole.

6. Safety assessments

Few AEs have been reported following mebendazole administration. The most common reported AEs are abdominal cramps, headache, diarrhoea, fever and fatigue [22, 28, 29]. The chewable mebendazole has previously caused convulsions but only in infants below the age of one year which are not included in this study. The concomitant administration of the chewable mebendazole and metronidazole has caused neutropenia and agranulocytosis [30]. The safety profile of mebendazole will be assessed through the recording, reporting and analysis of baseline medical conditions, a physical examination and active questioning at 3 and 24 hours post-treatment (see section 6.2).

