6.1. Adverse event definitions

The term “adverse event” could include any of the following events which develop or increase in severity during the course of the study, after administration of the study product:

- Any unfavourable and unintended signs, symptoms or disease temporally associated with the use of a medicinal product, whether or not considered related to the condition under study and the study product;
- Any abnormality detected during physical examination.

The medical conditions present at the initial trial visit that do not worsen in severity or frequency during the trial will not be defined as AEs but as be considered baseline medical conditions. For the purpose of this trial, disease progression and relapse will be considered as treatment failure, not as an AE.

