6.2. Methods of recording and assessing adverse events

Patients will be kept for observation for 3 hours following treatment for any acute AEs. 3h post-treatment participants will be actively questioned about any unfavorable changes in

the subject's condition. Any reported changes will be recorded as an AE, whether reported by the subject or observed by the Investigator. In case of any abnormal finding, the local study physician will perform a full clinical examination and findings will be recorded. An emergency kit will be available on site to treat any medical conditions that warrant urgent medical intervention. In addition, patients will be also interviewed by a nurse and/or a physician about the occurrence of AEs 24 hours. Information on all AEs (onset, duration, intensity and causality) will be immediately entered in the appropriate AE module of the CRF which is considered as a source document, regardless of whether they are thought to be associated with the study or the drug under investigation. Associated with the use of the drug means that there is a reasonable possibility that the event may have been caused by the drug (see also relatedness definitions below). For all AEs, sufficient information will be pursued and/or obtained so as to permit (i) an adequate determination of the seriousness of the event (i.e. whether the event should be classified as a SAE), (ii) an assessment of the casual relationship between the AE and the study treatments (i.e. whether the event should be classified as an adverse drug reaction), and (iii) an assessment of intensity of AEs by the study physician. Additionally, participants will be encouraged to notify study staff of any AEs that may occur outside of scheduled safety assessments. All SAEs, unexpected adverse drug reactions, or SUSARs must be reported as described in Section 6.3.

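### The only AE analysis in section 8.3 is a before-versus-after change; it states no chewable-versus-swallowable contrast, although the trial says it will compare safety

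*Combined protocol and SAP*

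**What the plan says.** The AE analysis is a single sentence in section 8.3: "AEs will be evaluated descriptively as the difference of proportion reporting AEs before and after treatment". The statistical analyses row of the synopsis contains no AE analysis.

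The aims are comparative in two places. The study objectives in the synopsis begin "To compare the efficacy and safety of two formulations of mebendazole", and section 2 (Background information) ends by saying "we will compare the efficacy, safety, and acceptability and age-appropriateness of the two tablets (swallowable and chewable) of mebendazole". The listed secondary objective, in the synopsis and in section 3, is softer: "To evaluate the safety and tolerability of the two formulations".

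Section 6.1 limits AEs to events that "develop or increase in severity during the course of the study, after administration of the study product". Conditions already present that do not worsen are classed as baseline conditions and not as AEs.

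On data collection, the synopsis row on measurements and procedures says "Participants will be interviewed before treatment for clinical symptoms and 3, and 24 hours after treatment to assess occurrence of adverse events (AEs". The opening of section 6 says that the safety profile will rest on "recording, reporting and analysis of baseline medical conditions, a physical examination and active questioning at 3 and 24 hours post-treatment". Section 6.2 adds "Information on all AEs (onset, duration, intensity and causality) will be immediately entered in the appropriate AE module of the CRF".

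**The concern.** The trial randomises children to two active formulations and has no untreated group. A change over time within an arm therefore mixes any effect of the tablet with background symptoms that come and go for other reasons. Randomisation protects only the comparison between arms, and section 8.3 does not ask for that comparison.

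The *before* term is also loose. Section 6.1 does not allow an AE before dosing, so the sentence either subtracts nothing or subtracts something other than AEs. Two analysts could follow the sentence faithfully and report different figures from the same data.

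What is at stake is the safety objective: a reader of the results might not find a stated difference between formulations or any measure of its uncertainty.

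**Working it through.** The documents state no AE rate, AE power or AE precision, so there is no figure of the plan's own to reproduce. The check is first a reading of the text and then a calculation of what the proposed contrast could show.

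**1. What the stated quantity is.** Write A for the proportion after dosing and B for the proportion before, with subscripts c (chewable) and s (swallowable).

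- Section 8.3, if applied by arm, gives A_c − B_c and A_s − B_s. Each is a within-arm change.
- The comparison announced in the synopsis and section 2 is A_c − A_s.
- Subtracting one change from the other gives (A_c − A_s) − (B_c − B_s). This is the arm contrast less the baseline imbalance. A reader could form it from by-arm results, but the plan does not state it and plans no CI for it.

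**2. What *before* can mean.**

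| Reading | Source | Consequence |
|---|---|---|
| AEs as defined in section 6.1 | Only post-dose events qualify | B = 0 by definition, and the figure is just the post-dose AE proportion |
| Symptoms at the pre-dose interview | Synopsis, measurements and procedures; section 6 plans analysis of baseline conditions | B is a symptom proportion, not an AE proportion |

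The second reading is the likelier one, because the first makes the subtraction pointless. It still fits section 6.1 poorly. An unchanged pre-dose symptom is already left out of A by the AE definition, so subtracting B removes it a second time. Neither reading yields A_c − A_s.

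**3. Precision of the missing contrast.** Inputs:

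- n = 200 per arm (section 8.2), taking all randomised children as treated.
- AE rates of 10% and 20% are assumptions. Section 6 describes reported AEs as few but gives no rate.

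Formula for the 95% CI half-width: 1.96 × √[(p_c(1 − p_c) + p_s(1 − p_s)) / n].

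- 10% in both arms: 1.96 × √[(0.09 + 0.09)/200] = 0.059, or 5.9 points.
- 10% versus 20%: 1.96 × √[(0.09 + 0.16)/200] = 0.069, or 6.9 points.
- 20% in both arms: 1.96 × √[(0.16 + 0.16)/200] = 0.078, or 7.8 points.

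For a wider range of assumptions, 5% in both arms gives 4.3 points and 30% in both arms gives 9.0 points. These figures describe what the proposed table would deliver. They do not measure an error in the present text.

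**The case against.** The best defence is that the sentence is shorthand. AE analysis is openly descriptive, the plan has no AE hypothesis or AE sample-size target, and the secondary objective says only that safety will be evaluated. Treatment and AEs are recorded together in each child's CRF, so by-arm tables are easy to produce and probably intended. Side-by-side proportions would be a form of comparison. The pre-dose interview is an evident candidate for *before*.

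Much of this stands. A descriptive analysis is appropriate and no test is called for. By-arm tabulation is not ruled out, and the baseline is better described as uncited than as absent.

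It does not close the gap. Two statements promise a comparison of safety, and the one difference that section 8.3 names runs over time. The same section does specify a difference between arms for the ERRs, so silence on this point for AEs leaves the choice to the analyst.

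A reader might infer more: that both arms will be pooled, so that opposite changes cancel and a real difference between formulations is hidden. The documents do not support that. The ERR paragraph of section 8.3 works arm by arm, and the safety objective refers to both formulations, so pooling is an unlikely reading. A reader might also infer that the plan fixes the *before* proportion at zero. Section 6.1 permits that reading, but the interview in the synopsis makes it improbable.

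**Conclusion.** The point holds as a mismatch between aim and analysis. The plan says that it will compare the safety of two formulations, and its only AE analysis is a within-group change with a baseline that is not tied to any assessment. This is more than missing detail, because the quantity named is unsuited to the comparative aim under either reading of *before*.

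Its weight is moderate: it should be corrected, but it concerns the safety objective alone. The ERR analysis and the sample size do not change. The conclusion rests on the wording and not on any assumed AE rate. The half-width of about 6 to 8 points does depend on assumed rates of 10% to 20% and on 200 treated children per arm.

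The documents also differ on the timing of the safety endpoint and on the SAE reporting period. Those are separate consistency matters and add nothing to this point.

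**What to change.** Replace the AE sentence in section 8.3 with:

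> For each arm, the number and proportion of treated children with at least one post-dose AE (section 6.1) will be reported at 3 and 24 hours, with the chewable minus swallowable difference and 95% CI, as descriptive estimation without a formal test. Symptoms at the pre-dose interview will be tabulated by arm as baseline conditions; worsening of a pre-existing symptom will be counted as an AE only where pre-dose severity was recorded. Passively reported AEs and SAEs will be listed by arm.

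The clause on worsening is needed because the documents do not show whether pre-dose symptoms are graded; the CRF is not reproduced. Passive reports are listed and not turned into rates because they depend on a child or caregiver contacting staff.

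The cost is one sentence and one extra table. No visit is added: the 3-hour and 24-hour interviews are already planned, and onset, duration, intensity and causality are already recorded under section 6.2.
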